#### Outcome Measures:

1. **Pelvic Organ Prolapse Quantification (POP-Q):** This is a validated scale adopted by IUGA/ICS and described in their 2010 joint report. It aims to measure the degree of POP where the hymen is the fixed point of reference for description. (5)
2. **Modified Oxford grading system:** This applies a 6-point scale to rate the muscle strength of the pelvic floor where, strength is as follows:  
0 = no contraction; 1 = flicker; 2 = weak; 3 = moderate; 4 = good; 5 = strong (6)
3. **The Pelvic Organ Prolapse/Incontinence Sexual Questionnaire, 12 (PISQ-12):** This is a brief validated, reliable and responsive measure of women's sexual function in those with pelvic floor disorders. (7)
4. **Incontinence Severity Index (ISI):** This is a validated questionnaire that has been shown to correlate well with pad weighing tests. (8)
5. **Patient's Global Impressions of Improvement (PGI-I):** This is a validated 1-item questionnaire rating specific condition as perceived change in her condition in response to therapy for SUI. (9)
6. **The International Consultation Incontinence Questionnaire-Short Form (ICIQ- SF)** This validated scale is a condition-specific assessing QOL of women with urinary incontinence. The most recent Cochrane review on Biofeedback recommends using this scale in trials using biofeedback for urinary incontinence. (10,11)
7. **Female Sexual Function Index (FSFI):** A brief questionnaire measure of sexual functioning in women that assesses arousal, orgasm, satisfaction and pain. (12)
8. **European Quality of Life-5 Dimensions (EQ-5D):** Preference-based utility index algorithm used to calculate each subject's utility index and compare change in QALYs between treatment groups (13).
9. **Overactive Bladder Questionnaire- short form (OAB-q SF):** Symptom bother scale that captures the full spectrum of OAB symptoms and health related quality of life (14).

## **13. Data Analysis**

Data Analysis: Between and within group differences will be evaluated using Fisher's exact test for categorical variables and t-tests for continuous variables. If there are any baseline differences between groups, a multivariate analysis will determine the contribution of these differences to observed differences (if any) between groups.

Power Analysis: Power analysis was performed based on previously reported means and standard deviation for the ICIQ-SF questionnaire. The primary outcome of this study is improvement in incontinence quality of life as measured by the ICIQ-SF Questionnaire. We used the previously reported means and standard deviation for this questionnaire (10) from a prior RCT on biofeedback and pelvic floor exercises. We have assumed a change score of greater than 4 points to be significant between groups based on prior studies and the minimally important difference that has been previously established (11). To achieve significance for a non-inferiority study using these assumptions we would need 42 patients, 21 per group to detect this difference with alpha =0.05 and with 80% power. To allow for a dropout of 20% we will enroll at least 50 patients, but up to 75 to account for participants who are lost to follow up.

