## 1. Objectives

The objective of this research is to perform a non-blinded, non-inferiority randomized controlled trial to assess the quality of life (QOL) of women with stress urinary incontinence (leakage of urine with cough or sneeze) before and after conservative treatment with either pelvic floor physical therapy (PFPT) or home biofeedback. The target population are patients with stress urinary incontinence (SUI) who are seeking care and desire non-surgical management. Our central hypothesis is that home biofeedback will be non-inferior to pelvic floor physical therapy and both will equally improve quality of life for women with stress urinary incontinence. The specific aims are:

**Aim 1:** To compare quality of life, as measured by the International Consultation Incontinence Questionnaire-Short Form (ICIQ- SF), in women with stress predominant incontinence before and after PFPT versus home biofeedback application after 3 months of therapy. Secondary outcomes related to this aim include improvements in urinary incontinence severity as measured by the Incontinence Severity Index (ISI) and desire to pursue additional therapy (such as pessary or surgery) at the conclusion of the study.

**Hypothesis:** Home biofeedback will demonstrate equal improvement in QOL in women with SUI compared to PFPT.

**Aim 2:** To perform a comparative analysis of cost between PFPT treatment and home biofeedback for stress predominant incontinence as well as patient preference for either PFPT vs home biofeedback. **Hypothesis:** Home biofeedback will be less expensive than PFPT due to decreased copays, driving to visits, with similar success rates and women will prefer to have home therapy.

**Aim 3:** To determine whether patients experience improvement in sexual function following treatment using the Pelvic Organ Prolapse Incontinence Sexual Questionnaire- 12 and Female Sexual Function Index (FSFI). **Hypothesis:** Both groups will report improved sexual function.

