### **3. Study Design**

We plan to perform an unmasked, non-inferiority randomized controlled trial to determine if quality of life is improved with use of PFPT or home biofeedback linked to smartphone for stress urinary incontinence. The target population are those patients with stress urinary incontinence who present to the urogynecology clinic either at University of New Mexico Hospital (UNMH) or Sandoval Regional Medical Center (SRMC). Women will be informed which arm of the study they are randomized to as this is required for treatment. Masking is not possible with this study design, as participants either do or do not receive a biofeedback device. All women will give written consent prior to enrollment.

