## 5. Number of Subjects

The primary outcome of this study is improvement in incontinence quality of life as measured by the ICIQ-SF Questionnaire. We used the previously reported means and standard deviation for this questionnaire (3) from a prior RCT on biofeedback and pelvic floor exercises. We have powered the study based on a 4-point difference as significant between groups. This 4-point difference used for the power calculation is based on prior studies and the minimally important difference that has been previously established (4). To achieve power for this non-inferiority RCT demonstrating a difference between groups of less than 4 points we need 21 patients per group (biofeedback versus PFPT) to detect no difference with an alpha =0.05 and

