### 7. Study Endpoints

The **primary endpoint** of our study is to determine the 3 month change in ICIQ-SF score between the women who undergo PFPT compared to those who undergo home biofeedback therapy for stress urinary incontinence. Our secondary endpoints include patient report of symptomatic cure or improvement and cost effectiveness between techniques and cost of intervention. Our **exploratory endpoints** are to investigate compliance with treatment between groups, preference if given choice between options, and differences in sexual function 3 months after initiation of therapy between the two groups. Desire for further treatment will also be assessed.

Given the extremely low-risk nature of the therapeutic interventions, we do not have any **safety endpoints**.

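### The trial is designed and sized as non-inferiority with a 4-point limit, but the planned t-test never uses that limit and cannot establish non-inferiority

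*Combined protocol and SAP*

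**What the plan says.** The design is stated consistently. Section 1: "Our central hypothesis is that home biofeedback will be non-inferior to pelvic floor physical therapy". Section 3: "We plan to perform an unmasked, non-inferiority randomized controlled trial". Section 12 repeats the label. The primary endpoint (Section 7) is to "determine the 3 month change in ICIQ-SF score between the women who undergo PFPT compared to those who undergo home biofeedback therapy".

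Section 5 uses 4 points as a margin, though it does not use that word: "To achieve power for this non-inferiority RCT demonstrating a difference between groups of less than 4 points we need 21 patients per group". It then describes the aim as being "to detect no difference with an alpha =0.05 and" 80% power. Section 13 gives the same inputs but presents more than 4 points as the difference that counts as significant between groups: "To achieve significance for a non-inferiority study using these assumptions we would need 42 patients, 21 per group to detect this difference".

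The method for the primary comparison is one sentence in Section 13: "Between and within group differences will be evaluated using Fisher's exact test for categorical variables and t-tests for continuous variables". Section 13 adds a multivariate analysis if the arms differ at baseline, and a cost and QALY comparison. Neither uses the 4 points.

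**The concern.** A non-inferiority claim requires rejecting the hypothesis that biofeedback is worse by the margin or more. A t-test of zero difference addresses another hypothesis, and neither of its outcomes answers the trial's question:

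- **p > 0.05** may mean only that the data are too few or too noisy.
- **p < 0.05** may accompany a deficit that lies wholly inside the margin.

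If absence of significance is taken as success, the chance of a false claim is one minus the power of the t-test, not the stated alpha. Dropout and noisy measurement then make the claim easier. The two power statements do not settle the matter, since one speaks of detecting no difference and the other of detecting a difference.

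**Working it through.** **Inputs from the documents.** 21 per arm, 4 points, alpha 0.05, power 80% (Sections 5 and 13); 20% dropout, 50 to 75 enrolled.

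**Not given, so assumed.** The SD (range 3 to 6 examined), the sidedness of alpha (one-sided 0.05 or 0.025), and the true difference used for power (0). Let d be biofeedback's deficit: mean ICIQ-SF improvement on PFPT minus mean improvement on biofeedback.

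**Step 1. The plan's own figure.** Without an SD, 21 per arm cannot be checked forward, so I solved for the SD. With the normal formula, n = 2·SD²·(z₁₋α + z₀.₈₀)² / 4², so SD = 4 / [(z₁₋α + 0.842)·√(2/21)]:

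- one-sided 0.05: 4 / [(1.645 + 0.842) × 0.3086] = 5.21
- one-sided 0.025: 4 / [(1.960 + 0.842) × 0.3086] = 4.63

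These are the largest SDs that round up to 21. The noncentral t distribution with 40 df gives **5.12** and **4.51**, used below.

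The figure of 21 does not show which test was intended. At SD 4.6 the normal formula gives 21 per arm both for non-inferiority at one-sided 0.025 and for an ordinary two-sided 0.05 test to detect 4 points.

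**Step 2. False claims if p > 0.05 is read as non-inferior.** Take d = 4, exactly at the margin. The standard error is SD·√(2/n) and the noncentrality is 4/SE. For SD 5.12 and n = 21, SE = 1.580 and the noncentrality is 2.53, against a two-sided critical value of 2.021 on 40 df. The probability of a non-significant result is:

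| SD | 16 per arm | 20 per arm | 21 per arm | 30 per arm |
|---|---|---|---|---|
| 3 | 5% | 2% | 1% | <1% |
| 4 | 22% | 13% | 12% | 3% |
| 4.51 | 32% | 22% | 20% | 8% |
| 5.12 | 43% | 33% | 31% | 16% |
| 6 | 55% | 46% | 44% | 28% |

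Twenty per arm is what 25 per arm leaves after 20% dropout; 30 per arm is 75 enrolled with the same dropout. Comparing the confidence limit with 4 points holds this error at 5% (one-sided 0.05) or 2.5% (one-sided 0.025) in every cell.

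**Step 3. The two rules can disagree in either direction.** With 21 per arm and an observed deficit of 2 points:

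- SD 4.6: SE = 1.420, t = 1.41, p = 0.17. The upper limit is 2 + 1.684 × 1.420 = 4.39 (90% CI) or 2 + 2.021 × 1.420 = 4.87 (95% CI). Not significant, yet non-inferiority is not shown.
- SD 3: SE = 0.926, t = 2.16, p = 0.037. The upper 95% limit is 2 + 2.021 × 0.926 = 3.87. Significant, yet non-inferiority is shown.

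**Step 4. Sidedness.** At SD 5.12 and d = 0, 21 per arm gives 80% power at one-sided 0.05 but about 69% at one-sided 0.025.

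**The case against.** The strongest reply is that Section 13 names no null hypothesis. A t-test shifted by 4 points is also a t-test, and Section 5 states the aim clearly enough: "To achieve power for this non-inferiority RCT demonstrating a difference between groups of less than 4 points". Nor does any section say that p > 0.05 will be read as non-inferior, so the error rates in Step 2 describe a rule the protocol does not state. They also depend on an unknown SD and on final numbers: the table shows 1% at SD 3 with 21 per arm, and 8% to 16% at the two back-solved SDs with 30 per arm.

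Part of this stands. The zero null is inferred from the ordinary meaning of an unqualified t-test of differences. The rates are conditional on SD, sample size and how the p-value is read. Fisher's exact test does not bear on a continuous primary endpoint. The two power phrases may be loose drafting rather than two designs, since both call the trial non-inferiority and share the same inputs.

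None of it supplies what is missing. No shifted null, confidence limit or decision rule appears anywhere, and the supplementary analyses do not use the margin. That the false-claim rate can run from about 1% to over 50% with noise and completers is the defect: a pre-set alpha should not move with either.

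**Conclusion.** The concern holds, and this must be fixed. Followed as written, the primary analysis cannot support the conclusion the trial is designed to reach. If non-significance were taken as non-inferiority, a true 4-point deficit would be missed in about 20% to 31% of trials at 21 per arm, against a stated alpha of 5%. That range assumes an SD of 4.5 to 5.1, back-solved on the premise that 21 per arm was a correct non-inferiority calculation with a true difference of zero. The omission itself depends on none of these assumptions.

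**What to change.** In Section 13, define the primary analysis as the between-arm difference in mean 3-month ICIQ-SF improvement with a confidence interval, and conclude non-inferiority only if the limit for biofeedback's deficit is below 4 points. State the one-sided alpha once and use it for both the sample size and the interval: 0.05 goes with a two-sided 90% interval, 0.025 with a 95% interval. State the SD used. In Sections 5 and 13, replace the two phrases about detecting no difference and detecting a difference with this rule.

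The cost is wording in two sections, with no new data and no added patients. If 0.025 is chosen and 21 per arm was computed at 0.05, restate the power (about 69% at SD 5.12). Should the sponsor prefer to recover 80%, about 27 completers per arm would be needed at that SD: 27/0.8 = 33.75, so 34 per arm or 68 enrolled. That is within the ceiling of 75, but exceeds the 25 biofeedback devices budgeted in the Medical Devices checklist.

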## **12. Study Procedures**

This non-blinded, non-inferiority randomized controlled trial will be conducted at the UNM Eubank Clinic and SRMC Urogynecology clinic. Each site will recruit participants and we will plan to obtain up to 75 between the two sites. Collaborating investigators will be members of the Urogynecology Division at UNM HSC.

The primary aim of our study is to determine if quality of life is improved with use PFPT versus home biofeedback therapy alone in women with SUI. The target population will be patients with SUI who are seeking care. The current recommendation is to advise patient undergo conservative management with PFPT, try an incontinence pessary, or request the patient perform exercises at home. For all patients who present for treatment of SUI, we will take a thorough history and physical (including a POP-Q pelvic examination), score vaginal muscle strength based on Modified Oxford Grading Scale, perform a cough stress test to assess for SUI, and counsel the patient on all of her options including medical and surgical interventions.

If the patient is interested in conservative management and fulfills study inclusion criteria, we will then offer her the choice of volunteering for the study. All women will give written consent prior to their enrollment at this time and fill out questionnaires in the clinic. Research staff and clinicians will obtain consent and administer study questionnaires. After enrollment, participants will fill out baseline surveys, including the International Consultation on Incontinence Questionnaire- Short form (ICIQ-SF), Incontinence Severity Index (ISI), European Quality of Life-5 dimensions (EQ-5D), Overactive Bladder Questionnaire short form (OAB-q SF) Pelvic Organ Prolapse Incontinence Sexual Questionnaire (PISQ-12), and Female Sexual Function Index (FSFI). Data collected in addition to the above outcome measures includes patient demographics, medical/surgical History, and contact information, which are attached as supporting documents. This information will be collected from the patient on the day of enrollment and we will review the patient's medical record if information is missing or unclear.

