Three months after starting active treatment, all participants will have a return visit to discuss progress, which is consistent with our standard care for these patients. If the participant had a delay in starting PFPT, the follow up visit will occur 3 months after first PT appointment. At the 3 month visit the patient will complete the ISI, ICIQ-SF, EQ-5D, OAB-q SF, PISQ-12, FSFI, and PGI-I. We will also ask the patient which treatment she would prefer if given the option, the level of satisfaction she has with the current treatment, and if she is planning any future surgical procedures or treatment for her stress incontinence. A physical exam will assess pelvic floor strength using the Modified Oxford Grading Scale and a cough stress test will be performed. If the patient is unable to return to clinic, a member of the research team will call the patient to administer the surveys over the phone. If unable to contact the patient 3 times, we will discontinue attempts and the patient will be considered lost to follow up.

Table 1: Outcomes collected at various time points

	Baseline	3 months
Demographic and medical history	X	
ISI	X	X
Revised Oxford Scale	X	X
ICIQ-SF	X	X
EQ-5D	X	X

FSFI	X	X
OAB-q SF	X	X
PISQ-12	X	X
PGI-I		X
Follow up Questionnaire		X

Our primary outcome is changes in QOL at 3 months after treatment initiation as measured by the ICIQ-SF. It is our standard of care to see patients back at 3 months following SUI treatment initiation to assess for continued leakage and offer further conservative or surgical management. Therefore, as part of a secondary aim we will assess sexual function, compliance with treatment between groups, preference between 2 options, and desire for further treatment at this 3 month time point.

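### Section 13 assigns Fisher's exact test to within-group categorical change, but the two visits are the same women and the test has no paired form (minor)

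*Combined protocol and SAP*

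**What the plan says.** Section 13 (Data Analysis) covers both kinds of comparison in one sentence: "Between and within group differences will be evaluated using Fisher's exact test for categorical variables and t-tests for continuous variables". The protocol names no paired method for categorical data, and it does not say how a within-group table would be laid out.

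The within-group contrast is before against after. Aim 1 in Section 1 compares outcomes "in women with stress predominant incontinence before and after PFPT versus home biofeedback application after 3 months of therapy".

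Three measures recorded at both visits are, or could be, categorical:

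- **Cough stress test and Oxford grade.** At baseline the clinicians will "score vaginal muscle strength based on Modified Oxford Grading Scale, perform a cough stress test to assess for SUI". At 3 months, "A physical exam will assess pelvic floor strength using the Modified Oxford Grading Scale and a cough stress test will be performed". The Oxford grade is ordered; the Outcome Measures list says "This applies a 6-point scale to rate the muscle strength of the pelvic floor". Neither is named as an endpoint in Section 1 or Section 7, and the cough test is absent from Table 1 and from the Outcome Measures list.
- **ISI.** This is a named secondary outcome: "Secondary outcomes related to this aim include improvements in urinary incontinence severity as measured by the Incontinence Severity Index (ISI"). It is collected at both visits. The plan does not say whether it is analysed as a score or as categories.

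**The concern.** Fisher's exact test compares two independent sets of people. Applied to one arm at two visits, it either counts each woman twice as if she were two people, or, laid out the other way, answers a different question. The word t-test can be read as a paired t-test when the comparison is within a group. No such reading is available for Fisher's test, so this is not just shorthand.

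At stake are the within-arm p-values for these measures. With about 21 women per arm, the choice of test can move a result across 0.05.

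**Working it through.** **Inputs.** From the protocol: 21 evaluable and 25 enrolled per group, alpha 0.05 (Sections 5 and 13). The 21 was derived for the primary ICIQ-SF comparison. Its standard deviation is cited but not stated, so the 21 cannot be reproduced; it is used here only as the arm size. The plan gives no figure for any within-group categorical test. All rates, grade distributions and correlations below are assumptions. Tests are two-sided at 0.05.

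**1. One worked table.** Take 21 women, 15 leaking at baseline and 9 at 3 months.

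- If 6 improve and none worsens, exact McNemar gives 2 × 0.5^6 = 0.031. Fisher on the visit-by-outcome table gives 0.118.
- If 9 improve and 3 worsen, the margins are the same. Exact McNemar gives 0.146; Fisher is still 0.118, because it does not see who changed.

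**2. Binary outcome, visit-by-outcome layout.** With rates p1, p2 and within-woman correlation r, P(positive at both visits) = p1·p2 + r·√[p1(1−p1)p2(1−p2)]. For 0.75, 0.40 and r = 0.3 this is 0.300 + 0.3 × 0.2121 = 0.3636. So P(improve) = 0.75 − 0.3636 = 0.3864 and P(worsen) = 0.40 − 0.3636 = 0.0364. Summing over all possible tables gives the power for 75% to 40%:

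| Arm size, test | r=0 | 0.1 | 0.2 | 0.3 | 0.4 |
|---|---|---|---|---|---|
| 21, Fisher | 50% | 50% | 50% | 50% | 50% |
| 21, exact McNemar | 50% | 54% | 59% | 66% | 73% |
| 21, mid-p McNemar | 60% | 64% | 70% | 76% | 84% |
| 25, Fisher | 65% | 66% | 67% | 68% | 69% |
| 25, exact McNemar | 60% | 64% | 70% | 77% | 85% |
| 25, mid-p McNemar | 69% | 73% | 79% | 85% | 92% |

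With no change (70% at both visits, 21 women), as r goes from 0 to 0.4, rejection falls from 2.3% to 0.4% for Fisher, from 2.1% to 1.0% for exact McNemar, and from 4.1% to 2.8% for mid-p.

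**3. Every woman leaks at baseline.** Change can then only be from wet to dry. With 21 women and 5 dry, Fisher gives p = 0.048, exact McNemar 2 × 0.5^5 = 0.0625, and mid-p half of that, 0.031. So Fisher and mid-p reject from 5 dry women and exact McNemar from 6. If 30% become dry, power is P(X ≥ 5) = 80% for Fisher and mid-p, and P(X ≥ 6) = 64% for exact McNemar. With 25 women, Fisher at 5 dry gives 0.0502, so Fisher and exact McNemar both need 6 (81% each) and mid-p needs 5 (91%).

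**4. Baseline-by-3-month cross-table.** Here Fisher tests whether the two visits are associated. With 21 women and 50% positive at both visits, so no change, it rejects 19% of the time at r = 0.3 and 54% at r = 0.5.

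**5. Six ordered grades.** Assume 3/12/30/35/15/5% at grades 0 to 5 at baseline and a shift of 0.7 latent SD, so the mean grade rises from 2.6 to 3.4. These figures are simulated, with the exact test on the 2×6 visit-by-grade table against Wilcoxon signed-rank, at latent correlation 0 / 0.3 / 0.6.

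- Power, 21 women: Fisher 30 / 27 / 23%, Wilcoxon 51 / 65 / 84%.
- Power, 25 women: Fisher 35 / 34 / 31%, Wilcoxon 60 / 74 / 91%.
- No change, 21 women: Fisher rejects 4.8 / 3.7 / 2.6%, Wilcoxon 4.0 / 3.7 / 3.3%.

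The gap at correlation 0 comes from ignoring order. Its widening comes from ignoring pairing.

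**The case against.** The best counter-argument is that the harm is neither certain nor large.

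- **The cough test may start near 100% positive.** Section 4 uses it to confirm diagnosis and eligibility. A positive test is not a listed inclusion criterion, so this is an inference, but a reasonable one. Step 3 then applies, and Fisher has at least the power of exact McNemar. This stands, and it rules out any general statement that Fisher loses power here.
- **Fisher is not always worse calibrated.** With no correlation it does about as well as exact McNemar on binary data, and on ordered grades it is as close to 5% as Wilcoxon or closer up to correlation 0.3. With 25 women and correlation 0 or 0.1, it also beats exact McNemar on power in step 2, though not mid-p. This stands too.
- **The affected set is small.** Oxford grade could be treated as a score, and so could the ISI; the t-test would then apply. Section 7 says "Our secondary endpoints include patient report of symptomatic cure or improvement and cost effectiveness between techniques and cost of intervention", but the PGI-I, treatment preference and wish for further treatment are asked only at 3 months. Their group comparisons are between arms, where Fisher is valid.
- **Within-arm p-values do not answer a non-inferiority question.** This is true, and it is why the point is minor.

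None of this makes Fisher a test of within-woman change. In step 1 it returns one p-value for two different patterns of change.

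**Conclusion.** The rule as written is wrong for within-group categorical change: it names an independent-samples test for paired data. That conclusion rests on the text alone.

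The size and direction of the effect are conditional. With the visit-by-outcome layout and positive correlation, Fisher is conservative and usually less powerful (50% against 66% and 76% in the central binary case). With nearly all women leaking at baseline, it loses nothing against exact McNemar and equals or falls below mid-p (21 women: 80%, 64%, 80% for Fisher, exact McNemar and mid-p; 25 women: 81%, 81%, 91%). With the cross-table layout it does not test change at all. For ordered grades, part of the loss is due to ignoring order, not pairing.

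A reader might infer that these tests are always conservative and always lose power, or that the trial's main conclusion is at risk. The documents support neither. They give no layout, rates or correlations, and no stated hypothesis is shown to rest on a within-group Fisher test. The primary ICIQ-SF comparison, the between-group Fisher tests and the 21 per group are unaffected. Severity is minor.

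**What to change.** Amend Section 13 to:

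- limit Fisher's exact test to between-group comparisons;
- for within-group change in binary outcomes such as the cough stress test, use a McNemar test with the version fixed in advance (mid-p preferred at this size);
- for Oxford grade, and for the ISI if categorical, use Wilcoxon signed-rank or a marginal homogeneity test;
- state whether the ISI is analysed as a score or as categories;
- as a clarification only, say that the within-group t-test is paired.

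This costs one or two sentences, with no new data and no change to the sample size. Settling it before analysis also removes a choice that could otherwise be made after seeing the results.

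### Fisher's exact test, the only method planned for categorical variables, cannot test Aim 2's hypothesis that women prefer home therapy, because it compares arms and not the overall proportion with 50%.

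*Combined protocol and SAP*

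**What the plan says.** Section 1 gives Aim 2 two parts: a cost comparison, "as well as patient preference for either PFPT vs home biofeedback". Its hypothesis ends "with similar success rates and women will prefer to have home therapy". That is directional and is worded about women in general, not about one arm relative to the other.

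Section 12 describes the measurement at the 3-month visit: "We will also ask the patient which treatment she would prefer if given the option". No baseline preference question is described, and Table 1 lists the follow-up questionnaire at 3 months only.

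Section 13 sets the analysis in one general sentence: "Between and within group differences will be evaluated using Fisher's exact test for categorical variables and t-tests for continuous variables". The rest of that section covers adjustment for baseline imbalance, the power statement, cost and EQ-5D utilities. It gives no reference value, one-sample test or confidence interval for the proportion preferring home.

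The status of the endpoint differs by section. Section 7 lists "preference if given choice between options" among the exploratory endpoints; Section 12 says "as part of a secondary aim we will assess sexual function, compliance with treatment between groups, preference between 2 options".

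**The concern.** The hypothesis concerns a level: do more than half of women prefer home biofeedback to PFPT? A between-arm Fisher test concerns a contrast: is the answer associated with allocation? The two can point in opposite directions. If women in both arms agree that home is better, there is no contrast to find. If women tend to favour whatever they received, there is a large contrast and possibly no overall preference. The second pattern is plausible here, because the trial is unmasked and each woman is asked after three months of her own assigned treatment.

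At stake is the preference part of Aim 2. A non-significant Fisher result could be reported as no evidence of a preference when the preference is strong, and a significant one as evidence for home when there is none.

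**Working it through.** **Inputs.** Section 13 gives 21 evaluable women per group (42 in all) and alpha 0.05, with no sidedness stated; I use two-sided. That sample size was set for the ICIQ-SF. It cannot be reproduced, because the standard deviation is taken from a cited trial and not printed; here it serves only as a count of women. The plan gives no figure for preference, so every preference count and rate below is an assumption. I also assume a two-way answer (home or PFPT).

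**Step 1: what Fisher returns.** Let a and b be the numbers preferring home among 21 in the biofeedback and PFPT arms. When a + b = 21, the count a is hypergeometric under the null, with P(a = k) = C(21,k)·C(21,21−k)/C(42,21), and the two-sided p is twice the upper tail (at most 1). For 15 v 6 the upper tail is 0.0063, so p = 2 × 0.0063 = 0.013. The other p-values come from the same test with their own margins. The last column is the two-sided exact binomial test of (a + b)/42 against 0.5.

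| Home preferred, biofeedback v PFPT | Overall | Fisher p | One-sample p v 50% |
|---|---|---|---|
| 20/21 v 20/21 | 40/42 = 95% | 1.0 | 4 × 10⁻¹⁰ |
| 2/21 v 2/21 | 4/42 = 10% | 1.0 | 6 × 10⁻⁸ |
| 16/21 v 16/21 | 32/42 = 76% | 1.0 | 0.0009 |
| 11/21 v 10/21 | 21/42 = 50% | 1.0 | 1.0 |
| 14/21 v 7/21 | 21/42 = 50% | 0.063 | 1.0 |
| 15/21 v 6/21 | 21/42 = 50% | 0.013 | 1.0 |
| 17/21 v 4/21 | 21/42 = 50% | 0.0001 | 1.0 |

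The first two rows are decisive: near-unanimous support for the hypothesis and near-unanimous rejection of it give the same p-value. The last four rows show that an even overall split becomes significant only once it follows the arm to about 15 v 6.

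**Step 2: how often each test is significant.** Sum the binomial probabilities over all 22 × 22 outcomes (a, b) that meet the criterion. For the one-sample test, the smallest significant majority is 28/42 (p = 0.044), so its power at a true 75% is P(X ≥ 28 | n = 42, 0.75) = 0.919.

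| True rate preferring home, biofeedback / PFPT | Fisher p ≤ 0.05 | One-sample p ≤ 0.05 in favour of home |
|---|---|---|
| 75% / 75% | 2.3% | 92% |
| 70% / 70% | 2.3% | 74% |
| 50% / 50% | 2.0% | 2.2% |
| 60% / 40% | 15% | 2.0% |
| 70% / 30% | 63% | 1.4% |
| 80% / 20% | 97% | 0.6% |

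**Step 3: the proposed estimate.** With arm proportions p₁ and p₂, take p̄ = (p₁ + p₂)/2 and SE = ½·√[p₁(1−p₁)/n₁ + p₂(1−p₂)/n₂].

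- 16/21 v 16/21: p̄ = 0.762, SE = ½·√(2 × 0.762 × 0.238/21) = 0.066, 95% CI 0.762 ± 1.96 × 0.066 = 63% to 89%. Hypothesis supported.
- 17/21 v 4/21: p̄ = 0.500, SE = ½·√(2 × 0.810 × 0.190/21) = 0.061, 95% CI 38% to 62%. Not supported.

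The same enumeration gives a lower limit above 50% in 93% of trials at 75%/75%, and in 2.6% to 3.5% of trials across the four rows with a true overall rate of 50%.

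**The case against.** **Section 13 never assigns Fisher to this hypothesis by name.** True. Its sentence is generic, and one may read preference as having no planned analysis at all. Nothing says that a null Fisher result would be taken to mean women do not prefer home. On either reading, though, the section contains no method that addresses the hypothesis, and the correction is the same.

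**The sentence also covers within-group differences.** This does not help. Preference is recorded once, so there is no within-group change to test, and Fisher's test is neither a one-sample nor a paired test.

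**A reader might infer that Fisher is significant whenever preference is evenly split.** The calculations do not support that. A true 50% in both arms gives significance 2% of the time and a 60/40 mirrored split 15%. The 97% figure needs an 80/20 mirrored split, for which the documents offer no evidence.

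**A reader might infer that this part of Aim 2 would have no usable answer.** That is also too strong. The proportions, overall and by arm, can be reported from the data collected, and 76% in both arms would be visible whatever the p-value. What is missing is a commitment to that summary and to a threshold before the unmasked data are seen.

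**The response options are unknown.** This stands. The follow-up questionnaire is not reproduced; if it allows a no-preference answer, 50% is a natural reference only among women who state a preference.

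**Conclusion.** The point holds: the plan states a directional preference hypothesis and names no analysis that can test it. At the planned 21 evaluable women per arm, a true 75% preference for home in both arms would give a significant Fisher result about 2% of the time, against 92% for a one-sample exact test on the same 42 answers. In the other direction, Fisher can be significant with no overall preference, but only when preference clearly follows allocation. These sizes rest on assumed preference rates, a two-way answer and a two-sided 5% level; the mismatch between test and hypothesis does not.

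The weight is minor to moderate. Preference is unpowered, Section 7 calls it exploratory and Section 12 places it under a secondary aim. The ICIQ-SF non-inferiority conclusion is not affected.

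**What to change.** Add to Section 13, as an exception to the general rule for categorical variables:

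*Among women stating a preference, the proportion preferring home biofeedback will be estimated as the equally weighted average of the two arm proportions, with a 95% CI from the variance stratified by arm, and compared with 50%. The hypothesis is supported if the lower limit exceeds 50%. Each arm's proportion, and any no-preference answers, will be shown with exact 95% CIs. The between-arm Fisher test will be used only to describe whether preference follows allocation.*

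Equal weighting keeps unequal dropout from shifting the answer towards one arm's view. The simple normal interval can pass 100% when nearly all women agree (at 20/21 v 20/21 the upper limit is 0.952 + 1.96 × 0.033 = 1.02), so truncate it there; the exact by-arm intervals cover that case. Sections 7 and 12 should also give preference the same status.

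The cost is a few sentences and slightly more analysis. No new data, patients or procedures are needed.
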